5.2 Study design

This is a prospective randomised controlled trial to evaluate the differences in relapse after expansion treatment between a Hawley and a modified vacuum formed retainer.

The study will involve:

- a. **Clinical:** An upper and lower impression with alginate will be taken for dental cast and retainer construction. **This procedure is a normal procedure done in all orthodontic appointments upon removal of fixed appliances.** However one extra upper impression will be taken for the research. It will take approximately 5-10 minutes. **All retention appliances will be distributed within 24 hours after debonding. The retainers will be washed under tap water before delivering to the patient. When subjects are given the retainers, clinicians will provide post-debond instructions, where the patient has to wear the retainers for 24 hours except during eating and brushing their teeth. Researcher will send reminders of wearing retainer in 1-month interval to ensure they are following the instructions and to enquire if they have any problems.** The patients will be instructed to wear the retainers for 24 hours for the next 6 months and night-time only for month 7 to month 12. At a 3 month and 6 month follow-up, an upper alginate impression will be taken for a dental cast construction at each follow-up visit. **Clinical examination will allow clinician to detect relapse which is by examining the arch width.** The whole duration of participation of each patient may total up to 40 minutes overall. If any unknown allergic reaction to alginate impression occurs, the procedure will be terminated immediately and appropriate first aid action will be given to participant, however these will most likely be anticipated as these subjects have had impressions taken at the start of treatment.
- b. **Data Measurement:** Dental casts will be analysed using digital callipers and arch width will be recorded in the posterior region.
- c. **Data analysis:** Data will be analysed using SPSS. The descriptive statistics on group level at times corresponding to measurements at removal of fixed appliances (T0), 3 months post retention (T1), 6 months post retention(T2) and 12 months post retention(T3) will be calculated for each variable.

RELAPSE DUE TO POOR COMPLIANCE:

- Poor compliance can be detected by the clinician, such as poor adaptation to speech, appliance looks “clean”, patient unable to seat and remove the appliance, or appliance is lost and not looked after properly.
- Arch width reduced
- Retainer will not fit in mouth

RELAPSE DUE TO INTERVENTION

- Patient able to adapt to retainers well, good adaptation to speech, appliance looks used, patient able to seat and remove retainers easily
- Arch width reduced
- Retainer should still fit in the mouth if patient wears it all the time

Compliance can be confirmed by the use of Thermosensors. Thermo-sensor is not used in this study because it is costly, not entirely accurate and it will not reflect the real-life situation. Most clinical studies do not use Thermosensors to ensure compliance. Using sensors will give out the Hawthorne effect where subjects will tend to perform better since they are aware of the presence of thermos-sensors. This as mentioned earlier does not reflect the real-life scenario.

Monitoring for adverse events

T0: Removal of braces	T1: 3-month review	T2: 6-month review
-Duration: 10-20 minutes -Subjects who have had 3mm of expansion (compared with pre-treatment models) will be selected, subjects given 5-10 minutes to think if they want to participate -Impression will be taken for construction of retainer and study models which will take 5-10 minutes -Adverse reaction i.e. allergic reaction to the impression material will be monitored however this would have been anticipated or recorded in the notes as these patients	-Duration: 5-10 minutes -Subjects will be reviewed and any adverse effect such as relapse will be detected at this point -An upper impression will be taken -Adverse reaction i.e. allergic reaction to the impression material will be monitored however this would have been anticipated or recorded in the notes as these patients would have had impressions taken at the start of orthodontic treatment. -If any allergic reaction occurs, first aid	-Duration: 5-10 minutes -Subjects will be reviewed and any adverse effect such as relapse will be detected at this point -An upper impression will be taken -Adverse reaction i.e. allergic reaction to the impression material will be monitored however this would have been anticipated or recorded in the notes as these patients would have had impressions taken at the start of orthodontic treatment. -If any allergic reaction occurs, first aid


would have had impressions taken at the start of orthodontic treatment
 
-Using the randomized generator, patient will be allocated to either a:
 
1- Hawley retainer
 
2-Modified vacuum formed retainer
 
-If any allergic reaction occurs, first aid management will be provided and an alternative impression material will be used
	
management will be provided and an alternative impression material will be used
	
management will be provided and an alternative impression material will be used

--	--	--

5.3 Ethics

A detailed protocol, ethical approval and site approval will be obtained from the KKM Ethics Committee before the study commenced. This research has been approved by the UKM Research Ethics Committee (Ethical approval number, UKM PPI/111/8/JEP-2018-724). All researchers in the study will adhere to the Good Clinical Practice Guidelines. A letter of consent will be obtained from each participant after explaining the nature and purpose of the study in verbal and in written. The data from the study will be made into a report which may be published. Participant's identity will be private and confidential, and will not be reported in any form of report. During the study, with respect to method of retention, if found in any patient for the relapse with VFR to be significant; new Hawley retainers (2-3 days) or retreat of fixed appliances (estimated 6-12 months) without any charge will be provided to the patient. Should subjects develop complications related to the study, treatment will be given at no cost at Faculty of Dentistry UKM Kuala Lumpur but subject will have to bear the travel expenses. Although theoretically the material of Hawley is more durable, there are no high quality long term studies comparing durability of both Hawley and VFRs. In fact long term follow-up studies have shown Hawley to have more breakages (Hitchens et al 2007). However if it does break, since it is an investigative product, we will replace the retainer with Hawley and subject will be considered dropout. During or after the study is completed, at any point if the research results are validated and if the modified VFR were found to be significantly less retentive than the Hawley retainer, subjects will be informed of the findings and new Hawley retainers will be provided to the modified VFR

group free of charge. If subject is not contacted regarding the results, it would mean that the modified vacuum is just as superior as the Hawley and the subjects in the modified vacuum can continue to use their retainer.

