1.0 EXECUTIVE SUMMARY

Relapse is inevitable in orthodontic treatment. Teeth will want to return to their original position after fixed appliances are removed. Regardless with or without fixed appliances, changes and physiological relapse will still occur due to time and age changes. This is why retention is a crucial part in orthodontic treatment, where it would aim to maintain the corrections achieved after orthodontic treatment.

Literature regarding retainers is quite substantial, where a recent Cochrane review was published comparing the different types of retainers. However, evidence is lacking in terms of comparison of arch width relapse between modified vacuum formed retainers and Hawley retainers specifically in expansion cases.

This study aims to compare the relapse in arch width in expansion cases with modified vacuum formed retainers with palatal coverage versus Hawley type retainers in Unit Ortodontik Universiti Kebangsaan Malaysia (UKM), Klinik Pakar Ortodontik Klinik Kesihatan Bandar Botanik and Unit Pakar Ortodontik Klinik Pergigian Sungai Chua patients. Although other types of modified vacuum formed retainers effective for maintaining palatal expansion have been described, these retainers require a wire outlining the Cementoenamel junction of the teeth palatally. This technique requires experience of the technician, is at a higher cost and requires more lab time. The modified retainer that we described in this study would be as efficient and as quick as the normal vacuum formed retainers, which would usually take a couple of hours to make (same day or next day fit). The present practice at all 3 locations constructs Hawley and normal VFR retainers for all orthodontic patients. There are technicians and laboratory facilities to construct normal VFR as well as Hawley retainer. The only difference between modified and normal vacuum formed retainer is the outline of the retainers where the technician would trim the retainer, where it would cover the hard palate. Therefore it is only the location of trimming that is different using the same special trimming appliances for normal VFRs.

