cheaper, quicker and easier to fabricate. There is a small risk of relapse using the modified vacuum formed retainers in expansion cases, however as mentioned earlier a lot of studies show good maintenance of arch width in normal cases (6)(8)(9). If relapse does occur, we anticipate that it will be minimal and a new retainer or retreatment can commence to easily rectify the situation as the patients are reviewed every 3 months. Other advantage is that most patients would prefer the appearance of vacuum formed retainers and superiority in terms of incisor alignment (6)(10). Literature showed that 40%-60% of allergic reaction was caused by formaldehyde (11). Formaldehyde may be released from methacrylate-based dental materials, such as composites and denture bases (12). An vitro study reported that there was minimal leaching of formaldehyde from thermoplastic materials (e.g. VFRs) while it was found higher leaching from poly-methyl methacrylate (PMMA) based orthodontic materials of the powder and liquid type (e.g. Hawley retainers) (13). Up to date, there is no reported case of sensitivity and contact allergy to VFRs while there was reported case of oral lesion in patient with Hawley retainer (14).

Hawley retainer		
Characteristics	Benefits	Risks
Clasps and wires anchored in a relatively thick plastic body	Personal opinion: suggested retainer to maintain expansion (Blake & Garvey 1998) compared with normal VFR (not modified)	More likely to break (Hichens et al. 2007)
Steel wire run across front teeth	More durable from patients' perception (Saleh et al. 2017)	Higher cost (Hichens et al. 2007) Require greater man power (Hichens et al. 2007) More difficult to fabricate (Saleh et al. 2017) Less aesthetic (Saleh et al. 2017) Heavier (Saleh et al. 2017)

Normal & Modified vacuum-formed retainer		
Characteristics	Benefits	Risks
Made up of thin and strong copolyester plastic sheets	Low cost (Hichens et al. 2007)	Less durable from patients' perception (Saleh et al. 2017) – Normal VFRs
Transparent	Easy to fabricate (Hichens et al. 2007)	
	Require less man power (Hichens et al. 2007)	
	More aesthetic (Saleh et al. 2017)	
	Lighter (Saleh et al. 2017)	
	Less likely to break (Hichens et al. 2007)	

Blake, M. & Garvey, M. T. 1998. Rationale for retention following orthodontic treatment. *Journal of the Canadian Dental Association* 64(9): 640–643. Retrieved from <http://www.ncbi.nlm.nih.gov/pubmed/9812432>

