- c. Undergone expansion treatment in the upper arch causing an arch width increase of 3-10mm, either using a Quadhelix, Rapid Maxillary Expansion, expansion with archwires, or URA with midline screw. Patients' interarch measurements at the time of debond will be compared with their interarch measurements using the pre-treatment model available at the clinic.
- d. No chronic medical conditions

The criteria for suspending or terminating the study are:

- a. Relapse due to compliance issue
- b. Relapse due to investigative product
- c. Subject did not come for follow-up

The subject withdrawal criteria are:

- a. Voluntary

If relapse is found and/or if subjects request to withdraw from the study, subjects will be informed that they will not need to take impressions at follow-up but they still can make appointment with their orthodontist for a normal retainer review. If insignificant relapse is found, new Hawley retainers will be provided free of charge. If significant relapse is found in subjects from intervention group, free treatment will be provided. The withdrawn subjects will not be replaced and an Intention to Treat analysis (ITT) will be done.

The generation of randomization sequence will be performed in blocks of 12 to ensure that equal number of patients was allocated to each of the two retention groups. A randomized generator will be used for allocation. In this multi-centre trial, a centralized randomization technique which incorporated external involvement is used. Individuals who recruit subjects from each centre will contact a central methods centre by phone after patient enrolled in order to prevent selection bias and protect the assignment sequence until allocation. Calibrated researcher will collect the study models which the ID and intervention are covered by opaque tape once they are ready for measurement. Only one dental cast at a time will be picked out of its box without showing any previous measurements. Two dental casts from the same patient will not be measured in connection with each other. Due to the prospective nature of the study, it was inconvenient to anonymize dental casts from the start of the study.

Hawley retainer
(coverage)

Normal VFR retainer

Modified VFR (palatal

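### Rules that class a broken retainer as a dropout and end impressions on relapse, read naturally, lose later casts and do not fit the promised intention-to-treat analysis

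*Combined protocol and SAP*

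**What the plan says.** Section 5.3 (Ethics) discusses durability, remarking that "there are no high quality long term studies comparing durability of both Hawley and VFRs" and that the Hawley has shown more breakages. It then sets a rule for a retainer that breaks: "since it is an investigative product, we will replace the retainer with Hawley and subject will be considered dropout". The pronoun is not tied to a named retainer.

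Section 5.1 (Participants Sampling) promises ITT: "The withdrawn subjects will not be replaced and an Intention to Treat analysis (ITT) will be done". Its only withdrawal criterion is voluntary withdrawal, and breakage is not among its suspension or termination criteria. The same section provides that, if relapse is found or a subject asks to withdraw, "subjects will be informed that they will not need to take impressions at follow-up". A new Hawley or free treatment may follow.

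Section 5.4.1 plans casts at debond and at 3, 6 and 12 months. Section 5.4 gives a normality test and one-way analysis of variance, and no method for missing casts. The Introduction tables rate the normal and modified VFR as "Less likely to break" and the Hawley as "More likely to break".

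**The concern.** Breakage happens after randomisation and reflects how the device performs, which is part of what the trial compares. Relapse is the outcome itself. If either event ends cast collection, the later means rest on subjects whose retainers held and who had not been found to relapse. An ITT analysis cannot use outcomes that were not collected, and casts not taken cannot be recovered.

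The undefined pronoun adds to this. On the VFR reading, one arm loses subjects by rule and no rule is given for a broken Hawley. If either retainer is meant, both arms lose subjects. With three sites, the rule could be applied in different ways.

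**Working it through.** **Step 1: the texts side by side.**
- Breakage (5.3): the subject is a dropout. No section says that casts stop or that data are excluded. The usual meaning of the word implies that casts stop.
- Relapse (5.1): the end of impressions is stated.
- ITT (5.1): promised, with no account of how missing casts enter it.
- A subject whose retainer breaks and who then relapses could lose casts by either route.

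**Step 2: the plan's own sample size.** Section 5.4 prints f = 0.42, 3 measurements, correlation 0.5, alpha 0.05 and a total of 32.
- Noncentrality = f² × N × m / (1 + (m − 1) × rho) = 0.1764 × 32 × 3 / 2 = 8.467; power 0.804. Both match the printout.
- Section 5.1 recruits 24 per arm for 16, an allowance of 1 − 16/24 = 33%.

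**Step 3: bias from breakage if later casts are lost.** Let pV and pH be the shares of the VFR and Hawley arms whose retainers break. Let d be how much more those subjects relapse than the rest of their arm. Each full-arm mean is the mean of the rest plus p × d, so dropping these subjects shifts VFR minus Hawley relapse by −pV × d + pH × d. The documents give no values for pV, pH or d, so all are assumed.

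| Reading | pV | pH | d (mm) | Shift (mm) |
|---|---|---|---|---|
| VFR only | 0.05 | 0 | 1 | −0.05 |
| VFR only | 0.10 | 0 | 1 | −0.10 |
| VFR only | 0.05 to 0.10 | 0 | −1 | +0.05 to +0.10 |
| VFR only | any | 0 | 0 | 0 |
| Either retainer | 0.05 | 0.10 | 1 | +0.05 |
| Either retainer | equal | equal | 1 | 0 |

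A negative shift flatters the VFR and a positive one the Hawley.
- Against the 2.0 mm target: 0.05/2.0 = 2.5% and 0.10/2.0 = 5%.
- Standard error at SD 2.0 mm and 24 v 24: 2.0 × sqrt(2/24) = 0.577 mm, so the shifts are 0.05/0.577 = 8.7% and 0.10/0.577 = 17.3% of one standard error.
- Wider assumptions, 10-30% breakage and 1-2 mm excess, give 0.1 to 0.6 mm. Nothing in the documents supports the upper end.

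I put no figure on the relapse rule. The plan gives neither a rate nor a threshold, and later casts would follow a new retainer or retreatment.

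**Step 4: power on the plan's inputs.** For unequal arms, N is replaced by 4 × n1 × n2 / (n1 + n2). The rows below 24 v 24 assume 20% other loss in both arms (24 × 0.8 = 19.2), then breakage, with arm sizes rounded.

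| Scenario | VFR v Hawley | Noncentrality | Power |
|---|---|---|---|
| No loss | 24 v 24 | 12.70 | 0.937 |
| Other loss only | 19 v 19 | 10.05 | 0.870 |
| + 5% VFR breakage | 18 v 19 | 9.78 | 0.860 |
| + 10% VFR breakage | 17 v 19 | 9.50 | 0.849 |
| + 10% breakage, both arms | 17 v 17 | 9.00 | 0.829 |
| + 30% VFR breakage | 13 v 19 | 8.17 | 0.790 |

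Of these scenarios, only heavy breakage on top of other loss falls below 0.80.

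**Step 5: dilution if switched subjects are kept.** If the true difference is 2.0 mm and a Hawley replacement undoes all of it, the ITT contrast shrinks by at most the switched fraction × 2.0 mm: 0.05 × 2.0 = 0.1 mm and 0.10 × 2.0 = 0.2 mm.

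**The case against.** The strongest reply is that the plan nowhere stops casts after breakage. Section 5.1 ends impressions only for relapse or a request to withdraw, and it promises ITT for those who withdraw. If casts continue after breakage, dropout is only a label. This stands in part: a reader might infer an outright contradiction with ITT, and the documents do not support that for breakage. They imply the loss without stating it. For relapse, the end of impressions is explicit.

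Second, the retainer is not seriously in doubt. A product under investigation that is replaced by a Hawley is most coherently the modified VFR. I accept that as the better reading. The preceding sentences concern both retainers and Hawley breakages, however, so the rule still needs a name in it.

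Third, the effect is small, every rate behind it is assumed, and the plan itself expects the VFR to break less often. That stands.

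Fourth, the relapse rule is a separate matter from breakage. It is, and it needs its own amendment, but it has the same consequence for the ITT analysis.

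Fifth, the remedy has a price: the largest possible dilution, 0.1-0.2 mm, can exceed the bias removed, 0.05-0.10 mm. That is true. Replacing like with like would avoid the dilution, but it keeps the subject on the investigative product, which the current text chooses to avoid. That is a trade-off, and I do not recommend it.

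**Conclusion.** The point holds in this limited form and should be fixed; confidence is moderate. Two rules, read naturally, remove later casts for reasons linked to the device or to the outcome, and this does not fit the promised ITT. The breakage bias is probably 0.05-0.10 mm, or 2.5-5% of the target, on an assumed 5-10% breakage and 1 mm excess relapse.

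Two stronger conclusions might be inferred, and neither is supported. One is that the rule favours the VFR: the sign depends on which retainer is meant and on whether subjects with breakages relapse more, less or the same. The other is that the trial would be underpowered: at 5-10% breakage with 20% other loss, power stays between 0.829 and 0.860.

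The reason to act is that the loss would be created by the plan's own rules and is cheap to avoid.

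**What to change.** 1. In 5.3, name the retainer and keep the Hawley replacement. Replace the closing words that make the subject a dropout with: *A subject in either arm whose retainer breaks stays in follow-up, has all remaining planned casts taken, and is analysed as randomised.*
2. In 5.1, replace the stop on impressions after relapse with: *A cast is taken when relapse is detected, before any new retainer or retreatment, and remaining planned casts are taken unless the subject refuses.* Mark casts taken after retreatment.
3. Report breakages and switches to a Hawley by arm, so that readers can judge the dilution.

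**Cost.** A few sentences, breakage and replacement dates on the visit form, and an ethics amendment, because subjects are currently told that impressions stop on relapse. The sample size does not change. At 5-10% breakage the casts kept are at most 24 × p × 3 = 3.6 to 7.2 if only VFR breakages count, or 48 × p × 3 = 7.2 to 14.4 if both arms do, out of 48 × 3 = 144 follow-up casts. Each takes 5-10 minutes. Relapse found between visits adds one cast. The ITT contrast may be diluted by up to 0.1-0.2 mm at 5-10% switching.

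These counts rely on the 12-month cast in 5.4.1. Section 5.2 schedules follow-up impressions only at 3 and 6 months, and its visit table ends at 6 months, so the 12-month impression should be added there too.

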A number of subjects who fulfil the criteria will be invited to participate in this study. The study will involve arch width analysis using study models pre, post-debond, 3 months review post-debond, 6 months review post-debond and 12 months review post-debond. All data will be analyses using Statistical Package for Social Sciences (SPSS). The arch width of subjects post-fixed appliances will be compared. Most studies compare the arch width, as well as lower incisor irregularity in evaluating relapse in different groups of retainers. However, there are currently no randomized control trials comparing expansion cases of Hawley vs vacuum formed retainers, hence why this study will be conducted.

We expect to see no difference between the modified vacuum formed retainer and Hawley retainer in terms of maintaining arch expansion post-orthodontic treatment. This would therefore mean that there would be a simpler method and would be a suitable more cost-effective alternative as compared to constructing Hawley retainers or adding a palatal wire on the vacuum formed retainers.

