3.0 HYPOTHESIS

There is a difference in the degree of relapse in terms of relapse of arch expansion between Modified Vacuum formed retainers and Hawley retainers.

NULL HYPOTHESIS

There is no difference in the degree of relapse in terms of arch expansion between Modified Vacuum formed retainers and Hawley retainers.

[figure not shown]

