5.0 METHODOLOGY

5.1 Participants Sampling

The sample will be selected from patients attending for orthodontic debond appointments at the Orthodontic Unit of Universiti Kebangsaan Malaysia (UKM), Klinik Pakar Ortodontik Klinik Kesihatan Bandar Botanik and Unit Pakar Ortodontik Klinik Pergigian Sungai Chua patients. The present practice at all 3 locations constructs Hawley and normal VFR retainers for all orthodontic patients. There are technicians and laboratory facilities to construct normal VFR as well as Hawley retainer. The only difference between modified and normal vacuum formed retainer is the outline of the retainers where the technician would trim the retainer, where it would cover the hard palate. Therefore it is only the location of trimming that is different using the same special trimming appliances for normal VFRs. Clinicians from KKM involved would be [name] [name] and [name] [name]. A screening will be done to select patients who are suitable of the study. Only patients who fulfil the criteria will be invited to participate in this study. Participant will be approached in the dental chair once deemed suitable, and will be given 5-10 minutes to decide on participation of the study. Consent will be gathered from the patients or the carer if the patient is below 18 years of age. The patients will then be randomly allocated into two groups using a randomized number computer generator, either the Hawley or the modified vacuumed formed retainers. The expected sample size to be of statistical significance will be calculated using the formula of sample size calculation relevant to this study. The sample size

calculation is based on a significance level of 0.05 and 80 percent power to detect a clinically meaningful difference of 2.0mm (SD=2.0mm) between the two groups in terms of arch width differences, where this difference are based on previous studies by Tynelius et al. (9) and Shawesh et al. (15). The power analysis gave a total sample size of 16 patients in each group. To account for attrition, 24 patients will be recruited in each group

The inclusion criteria of the subjects that will be included in the study are:

- a. Patients who are at least 13 years old at time of debond.
- b. Treatment plan of extraction or non-extraction followed by straight wire appliances in the upper arch only or both arches

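### A non-significant difference test is read as proof that the modified retainer matches the Hawley, with no margin or confidence-interval rule to support it

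*Combined protocol and SAP*

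**What the plan says.** Section 3.0 states the null: "There is no difference in the degree of relapse in terms of arch expansion between Modified Vacuum formed retainers and Hawley retainers". The alternative is non-directional. Section 5.1 sizes the trial at a 0.05 significance level for "80 percent power to detect a clinically meaningful difference of 2.0mm (SD=2.0mm) between the two groups", which gives 16 per group. It then adds: "To account for attrition, 24 patients will be recruited in each group". Section 5.4 compares group means by one-way analysis of variance and prints a repeated-measures power calculation that also arrives at 32 patients in total. Nowhere is there a non-inferiority or equivalence margin, or a conclusion tied to a confidence interval.

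Two places attach a conclusion to the absence of a difference:

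- Section 5.3 says participants will be informed "if the modified VFR were found to be significantly less retentive than the Hawley retainer", and then: "If subject is not contacted regarding the results, it would mean that the modified vacuum is just as superior as the Hawley".
- Section 1.0 says: "We expect to see no difference between the modified vacuum formed retainer and Hawley retainer in terms of maintaining arch expansion post-orthodontic treatment". It continues: "This would therefore mean that there would be a simpler method and would be a suitable more cost-effective alternative".

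Section 5.3 also uses the key word for a single patient, "if found in any patient for the relapse with VFR to be significant", where no p-value can apply.

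**The concern.** The test in sections 3.0, 5.1 and 5.4 is coherent. The fault is in what is concluded when it fails to reject. Failure to reject means the data did not rule out zero; it says nothing about which deficits they did rule out. Under section 5.3, an inconclusive result and a result that truly shows similarity both lead to no contact, and both are read as parity.

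This bears on the trial's central question. Parity is the result the investigators expect and the ground on which the modified retainer would be put forward as a cheaper substitute. The rule also rewards imprecision: the fewer patients analysed, the more likely a real deficit is to pass as parity.

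**Working it through.** **Inputs.** Difference 2.0 mm, SD 2.0 mm, alpha 0.05, 16 per group needed and 24 recruited (5.1); f = 0.42, three measurements, correlation 0.5 (5.4). Two-sided testing is assumed from the non-directional hypothesis in 3.0. Results are given as 16 / 24 analysed per group.

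**1. The plan's own figures.** Normal approximation: n = 2 × (1.960 + 0.842)² × (2.0/2.0)² = 15.7, so 16 per group, as stated. Repeated-measures printout: λ = 0.42² × 32 × 3 / (1 + 2 × 0.5) = 8.4672, critical F(1, 30) = 4.1709, power 0.8039. Both reproduce, so the arithmetic is not in dispute.

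**2. Precision of one comparison.** SE = 2.0 × √(2/n) = 0.707 / 0.577 mm. Half-width of the 95% CI = t(0.975, 2n−2) × SE = 1.44 / 1.16 mm.

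- An observed difference near zero would exclude 2.0 mm.
- An observed deficit above 2.0 − 1.44 = 0.56 mm (or 2.0 − 1.16 = 0.84 mm) would not, even though it can be non-significant.
- A deficit just short of significance has an upper limit of about 2 × half-width = 2.9 / 2.3 mm.

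**3. Chance of no significant deficit.** Noncentral t with 2n−2 degrees of freedom and noncentrality (true deficit)/SE:

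| True deficit (mm) | 16 per group | 24 per group |
|---|---|---|
| 0 | 97.5% | 97.5% |
| 0.5 | 90% | 87% |
| 1.0 | 72% | 60% |
| 1.5 | 46% | 28% |
| 2.0 | 22% | 8% |

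**4. Chance of being read as parity while the upper 95% limit still reaches 2.0 mm** (2,000,000 simulated trials, SD estimated in each): 19% / 5% if the true difference is zero, 45% / 21% if it is 1.0 mm.

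**5. Repeated-measures readings** (mean of three visits, correlation 0.5). The variance of the mean is SD² × (1 + 2 × 0.5)/3. The two sample-size descriptions imply different SDs, so both are shown. If f = 0.42 stands for 2.0 mm, SD = 2.0/(2 × 0.42) = 2.38 mm.

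| SD (mm) | Half-width (mm) | Non-significant at 1.0 mm | At 1.5 mm | At 2.0 mm |
|---|---|---|---|---|
| 2.38 | 1.40 / 1.13 | 71% / 59% | 44% / 26% | 20% / 6% |
| 2.0 | 1.18 / 0.95 | 61% / 45% | 29% / 12% | 8% / 1% |

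**6. Several outcomes.** The plan has three widths and three follow-up visits and names none as primary. Suppose a significant deficit on any of the three widths at one visit triggers contact, with an equal deficit on each (200,000 simulated trials). With correlation 0.5 between widths, no contact occurs 50% / 35% of the time at 1.0 mm and 6% / 1% at 2.0 mm. Over correlations 0 to 0.8 the ranges are 38–59% / 22–45% and 1–11% / 0–3%.

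**The case against.** The strongest reply is that section 5.3 is ethics text about informing participants, not an analysis rule, and that the sections defining the test draw no conclusion of parity. Section 1.0 can also be read as rationale: if there truly is no difference, the cheaper device is suitable, which is a valid conditional. The word for significance may be meant clinically, as it is elsewhere in 5.1 and 5.3. If so, section 5.1 does offer 2.0 mm as a benchmark. At 2.0 mm the 22% miss rate with 16 per group is essentially the planned type II error, and an observed difference near zero, the expected result, would exclude 2.0 mm. The 72% / 60% figures concern a 1.0 mm deficit, which the plan does not call clinically meaningful. The repeated-measures analysis with SD 2.0 mm and the three-width reading give lower error rates. Individual relapse checks with free replacement or retreatment, and participants' right under 5.4 to ask for results, limit the consequences.

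Much of this is fair on size. None of it makes the inference valid. The sentence in 5.3 is the only place where the plan says what a result without a significant deficit would mean, and it does not separate an estimate near zero from one just short of significance. If the word is clinical, nothing links the 2.0 mm in 5.1 to the contact decision, so the parity statement has no decision rule. Safeguards for single patients do not correct a group-level conclusion.

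**Conclusion.** The concern holds. As written, the plan would let an imprecise result be presented as equal effectiveness, and this should be corrected before analysis. The size depends on the reading. For a true 1.0 mm deficit, the chance of no significant deficit is 72% / 60% on a single comparison and 61% / 45% on the most favourable repeated-measures reading; it is 50% / 35% if any of three widths can trigger contact at correlation 0.5. For a true 2.0 mm deficit, the corresponding figures are 22% / 8%, 8% / 1% and 6% / 1%. These rest on two-sided p<0.05, the plan's SD of 2.0 mm and the stated correlations. The logical fault rests on none of them; only its error rate changes.

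**What to change.** 1. In 5.3, delete the sentence that infers parity from no contact. Suggested replacement: *Absence of a statistically significant difference will not be taken as evidence that the retainers are equally effective.* What participants then do with their retainers is for the sponsor to decide.
2. In 1.0, reword so that suitability as an alternative does not follow from a non-significant result.
3. In 5.4, add: *The between-group difference in mean relapse (modified VFR minus Hawley; relapse = T0 width minus follow-up width) will be reported with its two-sided 95% confidence interval.*
4. If parity is to be claimed, allow the claim only when the upper limit of that interval lies below a non-inferiority margin that the sponsor justifies and fixes before analysis, for one named width and one named visit. Otherwise report the result as inconclusive or inferior.

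Items 1 to 3 change wording and reporting only and are enough if no parity claim is made. Item 4 does not require a larger trial, but the achievable power should be stated for the chosen margin. For a single comparison with true difference zero, one-sided 0.025 and SD 2.0 mm, power at 16 / 24 per group is 78% / 92% for a 2.0 mm margin, 54% / 72% for 1.5 mm and 28% / 40% for 1.0 mm. These margins are illustrative; the documents give none. The price is that an imprecise result can no longer be presented as parity.
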